4.8 Data analysis

Analysis of outcome data will be conducted using an intention to treat approach, with patients analysed according to their treatment assignment. It will not be possible to collect outcome data for those who discontinue participation in the study. The data collected from outcome measures will be presented using

summary statistics (number of responses, mean ± standard deviation (SD), percentage frequency) and differences between intervention and control calculated at each follow-up points along with 95% confidence intervals. As this is a feasibility study, it will not be powered to identify significant differences between intervention and control. However, this data will help inform treatment effect estimates and sample size requirements for a larger powered RCT.

Feasibility of a future RCT will be investigated using progression criteria designed according to The Consolidated Standards of Reporting Trials (CONSORT) extension for reporting feasibility trials (38). This will enable interpretation of the findings of the feasibility study and inform whether a larger powered RCT is possible. Progression criteria will be assessed on a traffic light system of green/amber/red zones (39). Successful outcome of the feasibility trial would be to have all criteria assessed as green zones, suggesting no adjustments would be required for a future RCT. It is anticipated that progression to a future RCT would still be possible with a combination of amber and green zones but with potential adjustments implemented to mitigate risks highlighted in this feasibility study. Any red zone criteria would indicate that either the RCT trial design, or processes, will need to be overhauled for any future definitive study. All thresholds have been set based on levels that would enable completion of the trial objectives (Green without adaptation, Amber with adaptations to trial processes, Red/stop would not be possible to complete):

Criteria	Green	Amber	Red
Recruitment of participants based on target of n=100	>75	50 - 74	<=50
	(75%)	(50 - 74%)	(<50%)
Intervention engagement: assessed by number of intervention	>=70%	50-69%	50%
participants who have used iSupport-PD			
Recruited participants completing 3-month follow-up	>=75%	50-74%	<50%.
Recruited participants completing 6-month follow-up	>=75%	50-74%	<50%.
Recruited participants completing 12-month follow-up	>=75%	50-74%	<50%.
Ability to collect outcome data (assessed on baseline and follow-up). Each	>=85%	70-84%	<70%.
outcome measure would be a candidate for removal in a larger RCT if less			
than 85% of participants attempt to complete a measure:			

In addition, data around the use of the iSupport-PD intervention for those in the intervention arm will be analysed and reported to identify potential barriers to participants in accessing the intervention. This may include information such as number of times iSupport-PD is accessed, time spent on each page, number of contacts with technical support.

5. Health Economics

A prospective economic evaluation will be rehearsed to develop and refine methods for a subsequent definitive trial. The focus will be on accurately identifying, quantifying, and valuing the additional costs of delivering the intervention and the potential resource implications versus usual care. The costing approach will incorporate an NHS and personal social care perspective. Resources utilised in the intervention and control group are anticipated to include factors such as cost of iSupport-PD, primary care, secondary care, and public and private social care. Resource use data will be collected from participant follow-up forms and expert opinion. Appropriate unit costs to be applied to resource use will be identified from a combination of local costings and national databases. All costs will be combined to rehearse the methods for total cost estimation in a subsequent definitive trial.

The feasibility of conducting a cost-utility analysis will be explored using Quality-Adjusted Life Years (QALYs) derived from the EQ-5D-5L collected at baseline, 3,6,12 months post-randomisation. In addition, the ASCOT carers questionnaire will be used to investigate the feasibility of conducting a cost-utility analysis using social QALY. Issues relevant to sensitivity analysis will be explored to help understand how best to deal with statistical imprecision and other uncertainties in the full trial. For example, data will be bootstrapped to account for the expected skewness evident in economic cost data. The data collected as part of this feasibility study could be used to inform subsequent pre-trial modelling.

6. Process evaluation

Alongside the feasibility study, a process evaluation will be conducted in line with MRC guidance for process evaluation of complex interventions and the new MRC framework for developing and evaluating complex interventions (20). Up to 20 trial participants will be selected to take part in semi-structured interviews to explore their views and experiences of using iSupport-PD. Purposive sampling will be used to recruit carers from a range of ages, genders, carer relationships, caring experiences, ethnic groups, and socioeconomic status, as well as carers with different patterns of intervention usage (e.g. high and low users) and across different trial arms and recruitment methods (e.g. NHS, Parkinson's UK). On recruitment, trial participants will be asked for their consent to be contacted by the research team about the interview study and they will provide the demographic data required for the purposive sampling.

Participants will be offered either a telephone or teams interview at time convenient for them. Interviews will be audio recorded and transcribed verbatim. Participants will be asked about their views and experiences of engaging with the intervention and its recommended activities, being in the trial, and caring for a person with PD with cognitive impairment and how the intervention may have changed their abilities to care and cope with this role. Topic guides will be driven by our initial programme theories and will explore potentially unintentional intervention outcomes (e.g. further exacerbating carer strain). Data collection will cease once data saturation is met and the research team are confident that they have recruited participants with a range of demographics and sufficient participants from underserved groups. Interviews will be audio-recorded and transcribed verbatim. Transcribing will either be completed by the researcher or by McGowan Transcriptions (a secure system that researchers at Southampton University have a confidentiality agreement with). Once downloaded the audio recording will be deleted. The transcript will then be anonymised, and any personal identifiers removed from transcripts. Transcripts will be saved onto a secure university account. Inductive reflexive thematic analysis will be carried out (40) to further refine our programme theory and identify future intervention modifications.

Objective usage data (e.g. frequency and length of use, modules/lessons/pages visited) will be collected automatically by the website to measure intervention engagement. Participants allocated to the intervention group will also be asked at 6 and 12 months to complete a self-report questionnaire assessing adherence to the behavioural techniques/activities recommended by the intervention (e.g. relaxation). We will also assess intervention reach, including the percentage of participants allocated to the intervention arm who accessed the intervention and a description of the sample characteristics of those who did or did not access the intervention.

7. Assessment of safety

We do not anticipate any adverse events as part of this intervention which consists of guidance and support in addition to usual care. However, we will collect information from participants including hospital admissions and other NHS and social care resource use. As this is a feasibility trial, no data monitoring committee will be used. However, once the feasibility trail (WS2) begins recruitment, there will be a update of trial progress and

discussion of any unanticipated harms that may occur with consideration of ongoing trial safety.

8. Project Management

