3.5 Randomisation procedure

Randomisation will be performed on a 1:1 basis by computer using dynamic allocation, in particular minimisation, to ensure groups are balanced for carer age, relationship to person with PD, gender, and baseline quality of life score. Use of dynamic allocation will also protect against subversion(25).

Randomisation will occur after participants complete the study validated questionnaires that include caregiver burden, caregiver mental wellbeing, caregiver quality of life, quality of caregiver relationship, and health and social care service usage. The outcome measures used are: 12-item Zarit scale, CES-D10, GAD-7, RS-14, Dyadic Relationship scale, PDQ-C, General Self-efficacy scale, positive aspects of caregiving scale, EuroQol EQ-5D-5L, Adult Social Care Outcomes Toolkit (ASCOT) for carers. In addition, they will be asked to complete a questionnaire that will collect health and social care resource use data. This data will provide a baseline assessment for each participant.

Allocation will be hidden using the sealed envelope method whereby the information needed for randomisation, collected at baseline, will be placed in an opaque sealed envelope by a researcher and given to a separate researcher to conduct the randomisation independently.

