4.4 Sampling and sample size

For a feasibility study, no formal sample size calculation is required. The aim for this study is to recruit 100 eligible participants (50 in each arm). From this we will be able to estimate a participation rate of 50% to within a 95% confidence interval of \pm 0% where the confidence interval is estimated as 1.96 x (p x (1-p)/n) (27). Furthermore, this sample size should be sufficient to estimate the standard deviation an effect size of the main outcome measures to enable a sample size calculation for the full-scale trial.

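### Section 4.8 names no adjustment for baseline or minimisation factors, so on its plain reading the 95% intervals for the arm differences are wider than needed (minor)

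*Protocol*

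**What the plan says.** Protocol section 4.8 presents outcome data as "summary statistics (number of responses, mean ± standard deviation (SD), percentage frequency"), together with "differences between intervention and control calculated at each follow-up points along with 95% confidence intervals". It names no model, baseline term or other covariate. It also does not call the differences unadjusted. The same section says the study is not powered for differences, but that the data will inform the effect estimate and sample size of a larger trial. Section 4.4 likewise justifies the 100 participants (50 per arm) partly by estimation of an SD and effect size for that purpose.

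On design, section 3.5 allocates 1:1 by "minimisation, to ensure groups are balanced for carer age, relationship to person with PD, gender, and baseline quality of life score". The full set of questionnaires is completed before randomisation: "This data will provide a baseline assessment for each participant". Section 4.7 places follow-up at 3, 6 and 12 months.

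**The concern.** When allocation is forced to balance on a prognostic baseline score, the arm difference varies less from trial to trial than under simple randomisation. The standard error of a raw difference does not reflect that, so its interval is too wide. Apart from minimisation, a baseline score that predicts follow-up removes residual variance if it is in the model, and that gain is forgone if it is left out.

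Two deliverables are affected. One is the precision of the arm differences, in a trial with at most 50 per arm. The other is the SD passed to the main trial. If that trial adjusts for baseline, it needs the residual SD, or equivalently the baseline to follow-up correlation, and section 4.8 lists neither.

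**Working it through.** The protocol states no precision for the arm differences, so there is no figure to reproduce. The only precision statement, in section 4.4, concerns the participation rate and does not bear on this point.

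**Inputs from the protocol:** 50 per arm (4.4); 1:1 minimisation on four factors (3.5); 95% intervals (4.8); 75% as the green threshold for 12-month follow-up (4.8), used here as a retention scenario: 0.75 × 50 = 37.5, about 38 per arm.

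**Assumed:** baseline to follow-up correlation r of 0.3, 0.5 or 0.7, since the documents give none.

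**Interval width.** In SD units, with n per arm:
- Unadjusted half-width = t × √(2/n). At n = 50: 1.984 × 0.2 = 0.397.
- Adjusted half-width = t × √(2/n) × √(1 − r²), with one fewer degree of freedom.

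| r | √(1 − r²) | Half-width, 50 per arm (raw 0.397) | Half-width, 38 per arm (raw 0.457) | Narrower by |
|---|---|---|---|---|
| 0.3 | 0.954 | 0.379 | 0.436 | 4-5% |
| 0.5 | 0.866 | 0.344 | 0.396 | 13% |
| 0.7 | 0.714 | 0.283 | 0.327 | 28-29% |

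Simulated adjusted half-widths at r = 0.7 were 0.284 to 0.285, which is about 28% narrower than 0.397.

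**Coverage for the minimised score.** Trials of 100 were simulated with minimisation on four factors, one of them the outcome's own baseline in bands, and an assumed 80% biased coin. The ranges below span several sets of runs, including 2,000 runs per correlation with two bands and 4,000 with two to four bands. At 2,000 runs the Monte Carlo standard error near 95% is √(0.95 × 0.05/2000), about 0.5 points.

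| r | Coverage of unadjusted 95% interval |
|---|---|
| 0.3 | 94.8% to about 96% |
| 0.5 | 95.9% to 97.3% |
| 0.7 | 97.9% to 98.2% |

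In the 2,000-run set, adjusted intervals covered 94.0% to 95.3% over r from 0.3 to 0.8. The mechanism also shows there: the raw standard error is √(2/50) = 0.200 SD, but the actual SD of the unadjusted estimate was 0.202, 0.188 and 0.170 at r = 0.3, 0.5 and 0.7.

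**Main-trial sample size.** N is proportional to variance, so sizing a baseline-adjusted trial on the raw SD inflates N by 1/(1 − r²): 1/0.91 = 1.10, 1/0.75 = 1.33, 1/0.51 = 1.96. As an illustration, take an assumed effect of 0.3 SD and 90% power: n per arm = 2 × (1.960 + 1.282)²/0.09 = 234 on the raw SD. Multiplying by 1 − r² gives 213, 176 and 120.

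**The case against.** The strongest reply is that this is read from silence. An adjusted model also yields a difference and interval at each visit, so the sentence in 4.8 is compatible with adjustment, and covariates are commonly left to an SAP, which is not shown here. A reader might infer that the protocol specifies unadjusted differences; it does not say so. That stands as a limit on the claim. What remains is that 4.8 does set out a method, raw summaries plus a difference per visit, and its natural reading is a raw difference despite the minimisation.

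Second, no decision rests on these intervals. The progression criteria concern recruitment, engagement, retention and completeness; no test is planned; and section 4.6 says secondary results are not intended to be reported. Over-wide intervals err on the cautious side. This stands and sets the severity.

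Third, nothing is lost for good, because the correlation and residual SD can be computed later from data already held. This also stands, but the SD and effect estimate are stated products of the study, so it is sensible to report them in a usable form.

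Finally, section 4.8 says "It will not be possible to collect outcome data for those who discontinue participation in the study", and a reader might infer that visit-by-visit differences discard the data of those who leave. They do not: section 3.7 keeps data up to withdrawal, so leavers count at each visit they attended. A longitudinal model would draw on those earlier visits when estimating later ones, which is a gain in use of information and not a rescue of deleted data.

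**Conclusion.** The point holds as a minor one. If the differences are raw, the intervals are wider than needed by an amount that depends on a correlation the protocol does not give: slight at 0.3, material from about 0.5 upward. Excess coverage applies to the minimised quality-of-life score and, in lesser degree, to outcomes correlated with the minimised factors; elsewhere the cost is efficiency only. Leaving out the adjustment does not bias the estimate.

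Two stronger readings are not supported. The formula 2Φ(1.96/√(1 − r²)) − 1 gives coverage of 97.6% at r = 0.5 and 99.4% at r = 0.7, but it assumes the baseline score is exactly balanced. Minimisation over four factors balances a banded score only in part, and the simulated values are lower. They rest on an assumed biased coin and banding, because the protocol states neither. Nor is the raw SD the wrong one to report: it is correct for an unadjusted main trial and conservative for an adjusted one, and section 4.4 does not say which analysis the main trial will use.

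**What to change.** In section 4.8, state that the difference and 95% interval at each follow-up are adjusted for the baseline value of that measure and for the four minimisation factors, without p-values. A mixed model using all available visits is one suitable way. Keep the raw summaries by arm, and report beside them the residual SD and the baseline to follow-up correlation for each measure, so that the main trial can be sized for either analysis. The cost is a few lines of text and minor programming; all the data are already to be collected.

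### The recruitment row of the progression table contradicts itself at 50 and at 75: its count line and its percentage line assign different zones

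*Protocol*

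**What the plan says.** Protocol section 4.4 sets the denominator: "The aim for this study is to recruit 100 eligible participants (50 in each arm").

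The first row of the table in section 4.8 is labelled "Recruitment of participants based on target of n=100". With its count bands, in the order green, amber, red, it reads "Recruitment of participants based on target of n=100 >75 50 - 74 <=50". A second line in the same cells gives the percentages 75%, 50-74% and <50%.

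The next row is engagement: "Intervention engagement: assessed by number of intervention >=70% 50-69% 50"%. Its red cell has no inequality sign. The follow-up rows at 3, 6 and 12 months share one pattern, for example "Recruited participants completing 3-month follow-up >=75% 50-74% <50"%. The outcome-data row is built the same way, with green >=85%, amber 70-84% and red <70%.

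The text above the table attaches consequences to the zones. For green: "Successful outcome of the feasibility trial would be to have all criteria assessed as green zones", in which case no adjustment is needed. A mix of amber and green is expected still to allow progression with adjustments. For red: "Any red zone criteria would indicate that either the RCT trial design, or processes, will need to be overhauled for any future definitive study".

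**The concern.** A progression rule should put every possible result in one zone, and only one, before the result is known. The recruitment row does not do this at either of its two cut-points, and it gives each cut-point two different readings within the same row.

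The zones lead to different conclusions. If 50 participants are recruited, amber supports a definitive trial with adjusted processes, while red calls for an overhaul of design or processes. If 75 are recruited, the count line supplies no zone, so it is unclear whether the all-green condition can be met. In either case someone would have to choose a reading once the total was known, which is what pre-set criteria are meant to prevent.

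This is not something a protocol can be said to leave to the statistical analysis plan. The protocol states the thresholds itself, describes them as already set, and states them inconsistently.

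**Working it through.** **Inputs.** Target 100 (sections 4.4 and 4.8). Recruitment bands by count and by percentage, and the follow-up bands for comparison (table in section 4.8). No sample-size formula applies; the check is to assign each possible count to the printed bands.

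**Count and percentage are interchangeable here.** Percentage of target = 100 x n / 100 = n. A count of 75 is 75% and a count of 50 is 50%, so any disagreement between the two lines is a true contradiction and not a matter of scale.

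**Assignment near the cut-points.** The percentage line prints green simply as 75%; it is read here as 75% or more, since otherwise 76% and above would have no zone.

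| Recruited | By count (>75 / 50-74 / <=50) | By percentage (75% or more / 50-74% / <50%) |
|---|---|---|
| 49 | red | red |
| 50 | amber and red | amber |
| 51 | amber | amber |
| 74 | amber | amber |
| 75 | none | green |
| 76 | green | green |

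- n = 75: 75 > 75 is false and 75 <= 74 is false, so no count band applies.
- n = 50: 50 <= 50 <= 74 is true and 50 <= 50 is true, so two count bands apply.

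Over all counts from 0 to 100 (101 values), the count line fails to give a single zone at exactly two, 50 and 75. The percentage line gives a single zone at all 101.

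**After alignment.** With green >=75, amber 50-74 and red <50, every count from 0 to 100 falls in one zone: 75 is green, 50 is amber, 49 is red. This is the pattern of the follow-up rows.

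**Engagement row.** If the red cell is read as <50%, then with 50 intervention participants:

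- 24/50 = 48%, red
- 25/50 = 50%, amber
- 34/50 = 68%, amber
- 35/50 = 70%, green

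Every result from 0/50 to 50/50 then has one zone.

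**The case against.** The strongest reply is that this is a typographical slip with an obvious repair. Only two counts are affected, the percentage line already resolves both, and the follow-up rows confirm that resolution. The criteria are also described as informing whether a larger trial is possible, not as a mechanical stop rule, and section 4.6 defines feasibility as a composite that includes matters outside this table, such as the suitability of the outcome measures and of the cost data.

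Much of that stands. The intended rule can be recovered, and the problem bites only if recruitment lands on exactly 50 or 75. But nothing in the protocol says that the percentage line governs. The signs on the count line (>75 and <=50) are fully printed, so lost characters do not explain the conflict. The table is one part of the feasibility judgement, but it is the part with stated thresholds and consequences.

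Two stronger readings are tempting and should not be adopted.

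- **Very low engagement escapes red.** Taken literally, a red cell of 50% leaves 0/50 to 24/50 with no zone and puts 25/50 in two: 26 of 51 possible results. That is not a credible reading. Red is the worst column, and the follow-up rows have red at <50% beneath the same amber floor of 50%. The cell evidently means <50%, and the sign may have been lost when the text was extracted from the PDF.
- **Whole-number bands leave gaps.** A retention of 67/90 = 74.4% lies between 74% and 75%. These bands are ordinary whole-percent notation: 74.4% rounds to 74% and is amber. A rounding convention can properly sit in an analysis plan that is not shown here, so this is not an error in the protocol.

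**Conclusion.** The concern holds for the recruitment row. Its count line and its percentage line disagree at 50 and at 75, which are 2 of 101 possible counts and both of the row's cut-points. At 50 the disagreement spans amber and red, so the conclusion could be progression with adjustments or overhaul. At 75 it decides whether the all-green condition is open to the trial.

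This rests on the target of 100 as the denominator, which the row states, and on reading the green percentage as 75% or more.

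The engagement red cell is a point to confirm, not a second broken rule. A reader might infer from it that the plan tolerates very low engagement, or infer from the whole-percent bands that the remaining rows are also defective; the table's own structure supports neither inference. The defect is narrow, but it lies in a stated decision threshold for the primary feasibility outcome, so it should be corrected.

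**What to change.** 1. Set the recruitment row to green >=75, amber 50-74, red <50, and print the same bands on the percentage line (>=75%, 50-74%, <50%). This matches the follow-up rows.
2. Check the engagement red cell against the source document. If the sign is missing there too, print <50%.
3. Optionally, write the percentage bands as continuous, for example amber >=50% to <75% in the follow-up rows, so that no rounding convention is needed. This is a tidy-up.

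The cost is a correction to one table. No sample size, data collection or analysis changes. The correction should be dated and made before the final recruitment total is known or, failing that, before the data are locked (section 10.3), with a note of whether the total was known at the time.

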10.1 Quality assurance and Quality Control of data

Trial processed and data will be monitored throughout the trial with updated provided monthly at the trial management group meetings. Data collected during the course of the trial will be checked during the trial to offer quality assurance. As this is a feasibility trial, quality assurance will also allow the team to assess issues such as incomplete data collection forms, which may suggest misunderstanding, unwillingness to complete certain questions, or misunderstanding of data collection forms. This will contribute to the findings of the feasibility study and allow flexibility and changes to trial processes during the trial (with changes to the protocol noted and ethical approval for adjustments sought where necessary.

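### The outcome-data progression row leaves its denominator open, so on some readings it clashes with the retention rows, and it counts attempted rather than scorable measures

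*Protocol*

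**What the plan says.** The progression table in Protocol section 4.8 has three retention rows: "Recruited participants completing 3-month follow-up", "Recruited participants completing 6-month follow-up" and "Recruited participants completing 12-month follow-up". Each is green at 75% or more, amber at 50-74% and red below 50%.

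The outcome-data row has different cut-offs: green at 85% or more, amber at 70-84%, red below 70%. It opens "Ability to collect outcome data (assessed on baseline and follow-up). Each" and goes on to make a measure a candidate for removal from the larger trial if less "than 85% of participants attempt to complete a measure".

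The same section attaches consequences to the colours. All green means that nothing needs adjusting. A mix of green and amber still allows progression with adjustments. For red, "Any red zone criteria would indicate that either the RCT trial design, or processes, will need to be overhauled". It also says that outcome data cannot be obtained from people who stop taking part.

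Section 4.6 lists completeness of data collection among the components of the primary feasibility outcome. Section 10.1 says that quality assurance will look at incomplete forms, which may point to misunderstanding, "unwillingness to complete certain questions, or misunderstanding of data collection forms".

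**The concern.** The retention rows name recruited participants as their denominator. The outcome-data row says only participants. Nothing in it limits the count to people reached at a visit, and someone who has left the study attempts nothing. If leavers stay in the denominator, attrition is scored twice, the second time against stricter cut-offs. The same loss to follow-up could then be acceptable in one row and a cause for overhaul in another, and sound measures could be listed for removal because people left rather than because the measure failed.

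The row also does not say whether baseline and follow-up are pooled or judged separately, or whether the colour applies to each measure or to the set. The choice of reading could therefore be made after the data are seen.

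The second problem lies in the numerator. The row is meant to show whether outcome data can be collected, but it counts attempts. A measure that most people start and many leave too incomplete to score would pass.

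**Working it through.** The thresholds are set rather than derived, so there is no figure in the plan to reproduce. The check is whether the rows can agree.

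**Inputs.** All cut-offs come from section 4.8. The target is 100 participants (section 4.4), with follow-ups at 3, 6 and 12 months (section 4.7). Let r be retention in percent.

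**Assumptions.** Retention is the same at each follow-up, everyone who completes a follow-up attempts every measure, and non-completers attempt none. Baseline is taken as 100%, since "Randomisation will occur after participants complete the study validated questionnaires".

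**Highest attainable attempt rate under three readings**

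- A: all recruited, each follow-up judged alone: r.
- B: all recruited, baseline and three follow-ups pooled: (100 + 3r)/4.
- C: those returning that visit's questionnaire: 100% for any r.

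| r | Retention row | A | B | C |
|---|---|---|---|---|
| 84% | green | 84%, amber | 88%, green | green |
| 80% | green | 80%, amber | 85%, green | green |
| 79% | green | 79%, amber | 84.25%, amber | green |
| 75% | green | 75%, amber | 81.25%, amber | green |
| 69% | amber | 69%, red | 76.75%, amber | green |
| 60% | amber | 60%, red | 70%, amber | green |
| 59% | amber | 59%, red | 69.25%, red | green |
| 50% | amber | 50%, red | 62.5%, red | green |

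Under A the clash covers retention of 75-84% (green against amber) and 50-69% (amber against red). Under B the 85% line is reached at r = (4 × 85 − 100)/3 = 80% and the 70% line at r = (4 × 70 − 100)/3 = 60%, so the clash covers 75-79% and 50-59%. Under C there is none.

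**How often this would show under A.** Take X as binomial with n = 100.

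- True retention 80%: P(X ≥ 75) = 0.913 for retention green, but P(X ≥ 85) = 0.129 for outcome data green.
- True retention 60%: P(50 ≤ X ≤ 74) = 0.982 for retention amber, and P(X ≤ 69) = 0.975 for outcome data red.

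**Partial responders.** Someone may attempt a measure without completing the follow-up. To lift reading A to a cut-off T, the share of non-completers who must do so is (T − r)/(100 − r):

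- r = 75, T = 85: 10/25 = 40%.
- r = 84, T = 85: 1/16 = 6.25%.
- r = 69, T = 70: 1/31 = 3.2%.
- r = 50, T = 70: 20/50 = 40%.

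The ceiling under A is therefore soft near the upper edge of each band and firm near the lower edge.

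**Numerator.** As an illustration with assumed figures, suppose 95% attempt a measure and 60% can be scored. The row as worded gives 95%, green. Counting scorable responses gives 60%, red. This does not depend on readings A to C.

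**The case against.** The best defence is that the row is there to pick out individual measures that people will not fill in. That purpose fits a denominator of those reached at the visit, and the change from recruited participants to plain participants may be deliberate. On that reading nothing clashes. Denominators are also often left to an analysis plan, and any such plan is not shown here. This stands as a reason not to call the rows contradictory outright. It does not settle the matter: the Protocol fixes the thresholds and the attempt wording itself, and its text allows readings that give green, amber or red on the same data.

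Four stronger conclusions are tempting and are not supported.

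- That 50-69% retention is automatically red. This needs reading A, and attempting is looser than completing, so a few partial responders could avert red near 69%.
- That the true green line for retention is 85%. It is 85% under A, 80% under B and unaffected under C.
- That sound measures would be discarded. The row only makes them candidates for removal.
- That baseline completeness tells nothing. Section 3.5 does not require every measure to be fully completed before randomisation, and section 4.8 does not restrict baseline to those randomised.

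On the numerator, it is fair to say that this row is not the only check, because section 10.1 has the team review incomplete forms. But that review has no threshold, whereas this row carries the colour and the removal rule.

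**Conclusion.** The point holds in a conditional form for the denominator and without condition for the numerator. The clash is real if all recruited participants are counted: 75-84% and 50-69% retention when each follow-up is judged alone, 75-79% and 50-59% when baseline and follow-ups are pooled. It vanishes if only those returning that visit's questionnaire are counted. The bands rest on equal retention across follow-ups, every completer attempting every measure and no attempts by non-completers; the pooled bands also need full baseline completion. The probabilities further assume reading A, a true retention of 80% or 60%, and 100 people in the denominator, which the Protocol does not establish for every visit.

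Whatever the denominator, the attempt count does not measure what the row is named for. Severity is moderate: one row needs rewording before progression is judged, and the trial's conduct is not affected.

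**What to change.** Restate the row, for each measure and separately at baseline, T1, T2 and T3, as: the percentage of participants returning that visit's questionnaire for whom the measure can be scored under its own scoring rules. For the EQ-5D-5L this means all five domains answered; for the resource-use form, a set of key items named in advance. Keep 85% and 70%, and apply the removal-candidate rule to this percentage. Attempt rates can be reported alongside. Attrition is then judged only in the retention rows.

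If all recruited participants are truly meant, say so, state whether visits are pooled, and align these thresholds with the retention rows. With visits judged singly, the clash goes only if both rows use the same pair of cut-offs or the outcome-data cut-offs are no higher than the retention ones.

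The cost is the wording of one table row. The drawback is that the stricter numerator may move some measures from green to amber.
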